14.3 Appendix 3: Revised Assessment in Neuro-Oncology (RANO) Criteria

Table 14-2 RANO definition

Table 3. Criteria for Response Assessment Incorporating MRI and Clinical Factors	
Response	Criteria
Complete response	Requires all of the following: complete disappearance of all enhancing measurable and nonmeasurable disease sustained for at least 4 weeks; no new lesions; stable or improved nonenhancing (T2/FLAIR) lesions; patients must be off corticosteroids (or on physiologic replacement doses only); and stable or improved clinically. Note: Patients with nonmeasurable disease only cannot have a complete response; the best response possible is stable disease.
Partial response	Requires all of the following: $\geq 50\%$ decrease compared with baseline in the sum of products of perpendicular diameters of all measurable enhancing lesions sustained for at least 4 weeks; no progression of nonmeasurable disease; no new lesions; stable or improved nonenhancing (T2/FLAIR) lesions on same or lower dose of corticosteroids compared with baseline scan; the corticosteroid dose at the time of the scan evaluation should be no greater than the dose at time of baseline scan; and stable or improved clinically. Note: Patients with nonmeasurable disease only cannot have a partial response; the best response possible is stable disease.
Stable disease	Requires all of the following: does not qualify for complete response, partial response, or progression; stable nonenhancing (T2/FLAIR) lesions on same or lower dose of corticosteroids compared with baseline scan. In the event that the corticosteroid dose was increased for new symptoms and signs without confirmation of disease progression on neuroimaging, and subsequent follow-up imaging shows that this increase in corticosteroids was required because of disease progression, the last scan considered to show stable disease will be the scan obtained when the corticosteroid dose was equivalent to the baseline dose.
Progression	Defined by any of the following: $\geq 25\%$ increase in sum of the products of perpendicular diameters of enhancing lesions compared with the smallest tumor measurement obtained either at baseline (if no decrease) or best response, on stable or increasing doses of corticosteroids*; significant increase in T2/FLAIR nonenhancing lesion on stable or increasing doses of corticosteroids compared with baseline scan or best response after initiation of therapy* not caused by comorbid events (eg, radiation therapy, demyelination, ischemic injury, infection, seizures, postoperative changes, or other treatment effects); any new lesion; clear clinical deterioration not attributable to other causes apart from the tumor (eg, seizures, medication adverse effects, complications of therapy, cerebrovascular events, infection, and so on) or changes in corticosteroid dose; failure to return for evaluation as a result of death or deteriorating condition; or clear progression of nonmeasurable disease.

NOTE. All measurable and nonmeasurable lesions must be assessed using the same techniques as at baseline.
Abbreviations: MRI, magnetic resonance imaging; FLAIR, fluid-attenuated inversion recovery.
*Stable doses of corticosteroids include patients not on corticosteroids.

[figure not shown]

Table 14-3 Summary of RANO response criteria

Table 4. Summary of the Proposed RANO Response Criteria				
Criterion	CR	PR	SD	PD
T1 gadolinium enhancing disease	None	≥ 50% ↓	< 50% ↓ but < 25% ↑	≥ 25% ↑*
T2/FLAIR	Stable or ↓	Stable or ↓	Stable or ↓	↑*
New lesion	None	None	None	Present*
Corticosteroids	None	Stable or ↓	Stable or ↓	NAT
Clinical status	Stable or ↑	Stable or ↑	Stable or ↑	↓*
Requirement for response	All	All	All	Any*

[figure not shown]
Abbreviations: RANO, Response Assessment in Neuro-Oncology; CR, complete response; PR, partial response; SD, stable disease; PD, progressive disease; FLAIR, fluid-attenuated inversion recovery; NA, not applicable.
*Progression occurs when this criterion is present.
†Increase in corticosteroids alone will not be taken into account in determining progression in the absence of persistent clinical deterioration.

Table 14-2 and Table 14-3 is described in Updated Response Assessment Criteria for High Grade Glioma: Response Assessment in Neuro-Oncology Working Group. Journal of Clinical Oncology, Vol 11, No 8 (August), 1993: pp 1466-1477.

14.4 Appendix 4: Karnofsky Performance Status Scale (for patients greater than 16 years old)

Table 14-4 Karnofsky Performance Status Scale

Able to carry on normal activity and work; no special care needed	100%	Normal; no complaints
	90%	Able to carry on normal activity; minor signs or symptoms of disease
	80%	Normal activity with effort; some signs or symptoms of disease
Unable to work; able to live at home and care for most personal needs; varying amount of assistance needed	70%	Cares for self; unable to carry on normal activity or work
	60%	Requires occasional assistance; able to care for most personal needs
	50%	Requires considerable assistance and frequent medical care
Unable to care for self; requires equivalent of institutional or hospital care; disease may be progressing rapidly	40%	Disabled; requires special care and assistance
	30%	Severely disabled; hospitalization is indicated though death not imminent
	20%	Very sick; hospitalization necessary; active supportive treatment necessary
	10%	Moribund; fatal processes progressing rapidly
	0	Dead

14.5 Appendix 5: Lansky Score (for patients less than or equal to 16 years old)

Table 14-5 Lansky score

100	Fully active, normal
90	Minor restrictions in physically strenuous activity
80	Active, but tires more quickly
70	Both greater restriction of play and less time spent in play activity
60	Up and around, but minimal active play; keeps busy with quieter activities
50	Gets dressed but lies around much of the day; no active play but able to participate in all quiet play and activities
40	Mainly in bed; participates in quiet activities
30	Bed-bound; needs assistance even for quiet play
20	Often sleeping; play entirely limited to very passive activities
10	No play; does not get out of bed
0	Unresponsive

14.6 Appendix 6: Medication and herbals to be excluded or to be used with caution

Any patient who requires a prohibited medication should not be enrolled on a trial for LEE011 until further information becomes available.

Note: This is not a comprehensive list of cytochrome P450 isoenzymes and QT prolongation medications. This is only meant to be used as a guide. Please contact the medical monitor with any questions.

CYP3A4/5

In order to avoid clinically significant drug-drug interactions, the co-administration of known CYP3A4/5 substrates with narrow therapeutic windows will be prohibited (Table 14-6). Additionally, considering LEE011 is a substrate of CYP3A4, strong inducers and inhibitors of CYP3A4 will also be contraindicated (Table 14-6). Medications that are moderate or weak inhibitors or inducers of CYP3A4/5, are permitted in this study, however they should be used with caution (Table 14-7). In addition, sensitive substrates of CYP3A4/5, that do not have a narrow therapeutic index are permitted, but should be used with caution (Table 14-7).

Table 14-6 List of contraindicated CYP3A substrates, inducers or inhibitors

Category	Drug Name
Strong CYP3A Inhibitors – AUC substrate increased by ≥ 5 fold	Boceprevir, indinavir, lopinavir, nelfinavir, ritonavir, saquinavir, telaprevir, Clarithromycin, telithromycin, troleandomycin, itraconazole, ketoconazole, voriconazole, posaconazole, mibefradil, nefazodone, conivaptan, grapefruit juice
Strong CYP3A Inducers – AUC decreased by $\geq 80\%$	carbamazepine, phenobarbital, phenytoin, rifabutin, rifampin, Avasimibe, ² St. John's wort
¹ CYP3A substrates with narrow therapeutic index (NTI)	alfentanil, fentanyl, pimozide, astemizole, terfenadine, cyclosporine, sirolimus, tacrolimus, dihydroergotamine, ergotamine, quinidine, cisapride
¹ Drugs whose exposure-response indicates that increases in their exposure levels by the concomitant use of potent inhibitors may lead to serious safety concerns (e.g., Torsades de Pointes). ² Herbal product This list of CYP substrates was compiled from the Indiana University School of Medicine's "Clinically Relevant" Table (http://medicine.iupui.edu/clinpharm/DDIs/ClinicalTable.aspx ; accessed April 4 th , 2012), from the FDA's "Drug Interaction Studies —Study Design, Data Analysis, Implications for Dosing, and Labeling Recommendations, DRAFT GUIDANCE, February 2012 (For further information, please see the FDA's website: http://www.fda.gov/downloads/Drugs/GuidanceComplianceRegulatoryInformation/Guidances/UCM292362.pdf (accessed April 04, 2012))"	

Table 14-7 List¹ of medications which are CYP3A substrates, inducers or inhibitors to be used with caution

Category	Drug Name
Sensitive CYP3A substrates ²	brotizolam, midazolam, triazolam, ebastine, felodipine, nisoldipine, quetiapine, lovastatin, simvastatin, alpha-dihydroergocryptine, budesonide, buspirone, darifenacin, dasatinib, dronedarone, eletriptan, eplerenone, fluticasone, lurasidone, perospirone, sildenafil, ticagrelor, vardenafil
Moderate CYP3A inhibitors – AUC substrate increased by 2 to 5 fold	Amprenavir, aprepitant, atazanavir, clozapine, cimetidine, ciprofloxacin, crizotinib, darunavir, diltiazem, domperidone, elvitegravir, erythromycin, fluconazole, fosamprenavir, imatinib, lapatinib, losartan, mianserin, mifepristone, naftidrofuryl, nifedipine, ondansetron, oxatomide, pazopanib, pirenzepine, raloxifene, sorafenib, ticlopidine, schisandra sphenanthera, tipranavir, tofisopam, verapamil
Moderate CYP3A Inducers - AUC decreased by 50-80%	Bosentan, efavirenz, etravirine, modafinil, nafcillin, ritonavir, talviraline, tipranavir
¹ Any drug mentioned in the above list should be contraindicated if they are excluded based on any other exclusion criteria as specified in Section 5.3 of the Study Protocol ² Sensitive substrates: Drugs whose plasma AUC values have been shown to increase 5-fold or higher when co-administered with a potent inhibitor. ³ Herbal product This list of CYP substrates was compiled from the Indiana University School of Medicine's "Clinically Relevant" Table (http://medicine.iupui.edu/clinpharm/DDIs/ClinicalTable.aspx ; accessed April 4 th , 2012), from the FDA's "Drug Interaction Studies —Study Design, Data Analysis, Implications for Dosing, and Labeling Recommendations, DRAFT GUIDANCE, February 2012 (For further information, please see the FDA's website: http://www.fda.gov/downloads/Drugs/GuidanceComplianceRegulatoryInformation/Guidances/UCM292362.pdf (accessed April 04, 2012))"	

CYP1A2

The co-administration of known CYP1A2 substrates with a narrow therapeutic index and agents that are strong inhibitors of CYP1A2 are to be used with caution ([Table 14-8](#)).

[figure not shown]

Table 14-8 List¹ of medications which are CYP1A2 substrates with narrow therapeutic index (NTI) or strong inhibitors of CYP1A2

Category	Drug Name
Strong CYP1A2 Inhibitors – AUC substrate increased by ≥ 5 fold	enoxacin, fluvoxamine
² CYP1A2 substrates with narrow therapeutic index (NTI)	alosetron, clozapine, duloxetine, clinafloxacin, melatonin, olanzapine, ramelteon, rofecoxib, tacrine, theophylline, tizanidine, zafirlukast

¹ Any drug mentioned in the above list should be contraindicated if they are excluded based on any other exclusion criteria as specified in Section 5.3 of the Study Protocol
 
² Sensitive substrates: Drugs whose plasma AUC values have been shown to increase 5-fold or higher when co-administered with a potent inhibitor.
 
This list of CYP substrates was compiled from the Indiana University School of Medicine's "Clinically Relevant" Table (http://medicine.iupui.edu/clinpharm/DDIs/ClinicalTable.aspx; accessed April 4th, 2012), from the FDA's "Drug Interaction Studies —Study Design, Data Analysis, Implications for Dosing, and Labeling Recommendations, DRAFT GUIDANCE, February 2012 (For further information, please see the FDA's website: http://www.fda.gov/downloads/Drugs/GuidanceComplianceRegulatoryInformation/Guidances/UCM292362.pdf (accessed April 04, 2012))", and from the University of Washington's Drug Interaction Database
	

BSEP transporter

In order to avoid clinically significant drug-drug interactions, the co-administration of known BSEP inhibitors causing further BSEP inhibition are to be used with caution ([Table 14-9](#)).

Table 14-9 BSEP transporter: List of medications causing inhibition to be used with caution

Drug Name	Drug Class
Bosentan	Antihypertensive
Cyclosporin A	Immunosuppressant
Fusidate	Antibiotic
Glibenclamide	Sulfonylurea
Lovastatin	Antihyperlipidemic
Nefazodone	Antidepressant
Rifampicin	Antitubercular
Ritonavir	Antiretroviral
Sulindac	Nonsteroidal anti-inflammatory
Troglitazone (TGZ-sulfate)	Anti-diabetic

QT prolongation

Due to the concern that LEE011 will cause QT prolongation, caution should be exercised with all medications that are known to produce this effect. Those known to have a strong signal will be prohibited ([Table 14-10](#)) and others are to be used with caution ([Table 14-11](#)).

[figure not shown]

Table 14-10 QT prolongation: List of excluded medications

Drug Name	Drug Class
Amitriptyline, Desipramine, Imipramine	Antidepressants
Chloroquine	Antimalarials
Chlorpromazine, Mesoridazine, Risperidone	Antipsychotics
Itraconazole, Ketoconazole	Antifungals
Tacrolimus, Arsenic trioxide, Domperidone	Miscellaneous drugs

Table 14-11 QT prolongation: List of medications to be used with caution

Drug Name	Drug Class
Dolasetron, Ondansetron, Tropisetron	Anti-emetics
Doxepin, Maprotiline, Venlafaxine,	Antidepressants
Gatifloxacin, Moxifloxacin, Sparfloxacin	Quinolone antibiotics
Halofantrine	Antimalarials
Pentamidine, Droperidol, Methadone, Bepridil	Miscellaneous drugs
Thioridazine, Ziprasidone,	Antipsychotics

14.7 Appendix 7: Prior calibration and operating characteristics of the Bayesian logistic regression model (BLRM)

Statistical model and dose recommendation

An adaptive BLRM with 2 parameters, guided by the EWOC principle, will be used to make dose recommendations and estimate the MTD/ RDE during the study. The use of Bayesian response adaptive models for Phase I studies has been advocated by the EMEA guideline on small populations, 2006 and by Rogatko et al (2007) and is one of the key elements of the FDA's Critical Path Initiative.

[figure not shown]
The adaptive BLRM will be fitted on the dose-limiting data (i.e. absence or presence of DLT) accumulated in cycle 1 throughout the dose escalation and the dose expansion parts of the study, for modeling the dose-DLT relationship of LEE011.

The DLT relationship in the escalation and escalation parts of the study will be described by the following Bayesian logistic regression model:

$$\text{logit}(\pi_{(d)}) = \log(\alpha) + \beta \log(d/d^*), \quad \alpha > 0, \beta > 0$$

where $\text{logit}(\pi_{(d)}) = \ln(\pi_{(d)}/(1-\pi_{(d)}))$, and $\pi_{(d)}$ is the probability of a DLT at dose d . Doses are rescaled as d/d^* with reference dose of $d^* = 580 \text{ mg/m}^2$. As a consequence α is equal to the odds of the probability of toxicity at d^* . Note that for a dose equal to zero, the probability of toxicity is zero.

If a different dosing schedule will be considered, a Bayesian Meta-analytic approach will be used to take into account historical data collected for the initially planned schedule in the actual study, in order to derive an informative prior estimation of the dose-toxicity relationship for the new dosing regimen.

Prior specifications

The Bayesian approach requires the specification of prior distributions for the model parameters. All information currently available about the dose-DLT relationship of LEE011 was summarized in a prior distribution. [REDACTED]

- [REDACTED]
- Estimation of the MTD/RDE in the dose-escalation part of the current study will take into account patients in the dose-determining set and will be based upon the estimation of the probability of DLT in the Cycle 1, [REDACTED] by 28 days.
- [REDACTED]
- For the pediatric population subject to inclusion/exclusion criteria studied in the current trial, it is expected that the probability of DLT within cycle 1 at any given LEE011 doses administered in mg/m^2 is similar to the probability of DLT within cycle 1 at the corresponding flat LEE011 dose administered in the adult population [REDACTED].

- [REDACTED]
 - [REDACTED]
 - [REDACTED]
- [REDACTED]
 - [REDACTED]
 - [REDACTED]
- [REDACTED]

[REDACTED]

[Redacted]

- [Redacted]
- [Redacted]
- [Redacted]
- [Redacted]

[Redacted]

[Redacted]

[Redacted]

- [Redacted]
- [Redacted]
- [Redacted]

[Redacted]

- [Redacted]
- For the remaining doses, the prior [Redacted]

[Redacted]

- [Redacted]

[Redacted]

[Redacted]

[Redacted]

[Redacted]

[Redacted]

[Redacted]

Hypothetical dose escalation scenarios

In order to show how the Bayesian model reacts, different hypothetical dose escalation scenarios were investigated. The design should make reasonable dose-recommendations during the clinical trial based on the observed DLTs. During the study, the decision to dose escalate after completion of a given cohort and the actual dose chosen for the subsequent cohort will depend on the recommendation of the BLRM per EWOC principle and medical review of available clinical and laboratory data.

Note that the next dose level is selected in concordance with the provisional dose levels specified in [Section 6.2.1](#) of the protocol, to mimic possible on-study escalation steps. For example, in scenario 1 (0/3 at 280 mg/m²), the next dose level is below the maximal increase allowed by the model and below the 100% increase limit. However, since this is one of the provisional dose levels suggested for the next cohort, it has been selected.

Additionally, for the scenarios in which a high toxicity rate is observed at the starting dose level (2/3 DLTs, scenario 3), a dose of 85 mg/m² has been added in order to show cases in which future re-escalations of the compound may be recommended.

Some scenarios to illustrate the dose escalation up to the third dose cohort are listed in [Table 14-15](#). Some scenarios illustrate the ability for the model to handle cohorts of different size.

[figure not shown]

Table 14-15 Scenarios

scenario	LEE011 dose	Npat	Ntox	Next dose level (NDL)	P(target) NDL	P(over) NDL	Median DLT rate
1	280 mg/m ²	3	0	420 mg/m ²	31.5%	7.5%	13.7%
2	280 mg/m ²	3	1	280 mg/m ²	43.3%	16.9%	19.5%
3	280 mg/m ²	3	2	85 mg/m ²	35.7%	25%	20.3%
4	280 mg/m ² 420 mg/m ²	3 3	0 0	630 mg/m ²	31.8%	10.2%	14.1%
5	280 mg/m ² 420 mg/m ²	3 3	0 1	420 mg/m ²	45.9%	10.8%	18.3%
6	280 mg/m ² 420 mg/m ²	3 3	0 2	280 mg/m ²	48%	15.4%	20.1%
7	280 mg/m ² 280 mg/m ²	3 3	1 0	420 mg/m ²	46%	13%	18.9%
8	280 mg/m ² 85 mg/m ²	3 3	2 0	210 mg/m ²	45.6%	22.7%	22%
9	280 mg/m ² 420 mg/m ²	3 6	0 2	420 mg/m ²	55.5%	13.9%	20.9%
10	280 mg/m ² 420 mg/m ²	3 6	0 3	280 mg/m ²	53.7%	15.2%	21.4%
11	280 mg/m ² 420 mg/m ² 630 mg/m ²	3 3 3	0 0 0	850 mg/m ²	25.3%	7.2%	11.9%
12	280 mg/m ² 420 mg/m ² 630 mg/m ²	3 3 3	0 0 1	630 mg/m ²	43.9%	14.2%	18.7%
13	280 mg/m ² 420 mg/m ² 630 mg/m ²	3 3 3	0 0 2	420 mg/m ²	48.7%	10.1%	18.6%
14	280 mg/m ² 420 mg/m ² 630 mg/m ²	3 3 6	0 0 2	630 mg/m ²	52.1%	16.4%	21.2%
15	280 mg/m ² 420 mg/m ² 630 mg/m ²	3 3 6	0 0 3	420 mg/m ²	53.2%	9%	19.2%
16	280 mg/m ² 420 mg/m ² 630 mg/m ² 420 mg/m ²	3 3 3 6	0 0 2 0	* 420 mg/m ²	31.3%	1.6%	13.2%

* the next dose level is selected in concordance with the provisional dose levels specified in [Section 6.2.1](#) but in this case intermediate doses between 630 mg/m² 420 mg/m² would be more appropriate and are allowed as per EWOC.

Within [Table 14-14](#), it can be seen that the model leads to decisions that are in agreement with clinical sense: progressive increase of the LEE011 doses if no DLT is observed, enrolling of a new cohort at the same dose level when 1/3 or 2/6 DLT's are reported, and decrease when more than 1 or 2 DLTs are reported in cohorts of 3 or 6 patients respectively.

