6.4.2 Concomitant therapy requiring caution

The following therapies are permitted in this study, however they should be used with caution:

- Medications that are moderate inhibitors or inducers of CYP3A4/5. (Refer to [Appendix 6](#)).

- Sensitive substrates of CYP3A4/5 that do not have a narrow therapeutic index (Refer to [Appendix 6](#)).
- Known BSEP inhibitors listed in [Appendix 6](#).
- Agents that are metabolized predominantly by CYP1A2 with a narrow therapeutic index and agents that are strong inhibitors of CYP1A2 listed in [Appendix 6](#).
- Medications that carry a moderate-low risk for QT prolongation listed in [Appendix 6](#).

Patients receiving such medications must be carefully monitored for potentiation of toxicity due to any individual concomitant medication, and may require dose titration of the drug substance.

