6.4.3 Prohibited concomitant therapy

The following therapies are prohibited:

- Strong inducers or inhibitors of CYP3A4/5. In particular EIAEDs. (Refer to [Appendix 6](#)).
- Substrates of CYP3A4/5 with narrow therapeutic windows (Refer to [Appendix 6](#))
- Medications that carry a strong risk for QT prolongation (Refer to [Appendix 6](#))
- Concurrent anti-neoplastic therapy, including radiotherapy
- Patients should be instructed not to take grapefruit products/juice, or Seville (sour) oranges/juice while receiving LEE011 treatment throughout the study due to its potential for CYP3A4/5 interaction.

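### Section 6.4.2 and Table 14-9 permit, with caution, four BSEP inhibitors that Section 6.4.3 and Table 14-6 prohibit, and Table 14-9 lacks the precedence footnote that Tables 14-7 and 14-8 carry

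*Protocol*

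**What the plan says.** Three places in the protocol govern co-medication during treatment.

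- **Section 6.4.2 (caution).** Its opening line reads "The following therapies are permitted in this study, however they should be used with caution". One item on its list begins "Known BSEP inhibitors listed in" and refers to Appendix 6. It makes no exception for a BSEP inhibitor that is prohibited on other grounds.
- **Section 6.4.3 (prohibited).** The list includes "Strong inducers or inhibitors of CYP3A4/5. In particular EIAEDs", CYP3A4/5 substrates with narrow therapeutic windows, and "Medications that carry a strong risk for QT prolongation". It states no exceptions.
- **Appendix 6 (Section 14.6).** The CYP3A4/5 text repeats the bans: "strong inducers and inhibitors of CYP3A4 will also be contraindicated", and "the co-administration of known CYP3A4/5 substrates with narrow therapeutic windows will be prohibited". Table 14-6 names the drugs. The BSEP paragraph then says that "the co-administration of known BSEP inhibitors causing further BSEP inhibition are to be used with caution" and points to Table 14-9.

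Footnote 1 to Tables 14-7 and 14-8 says that a listed drug is to be treated as contraindicated if a Section 5.3 exclusion criterion rules it out. Table 14-9 carries no such note. Appendix 6 opens by saying that a patient who needs a prohibited medication should not be enrolled, that the lists are a non-comprehensive guide, and that questions go to the medical monitor.

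**The concern.** A site that looks up one of these four drugs in the BSEP table finds it marked as usable with caution. The same site looking in the CYP3A table finds it contraindicated. Nothing attached to Table 14-9 says which entry governs.

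The naming makes a one-sided lookup easier. Rifampicin and cyclosporin A appear under those names only in Table 14-9, while the prohibited table uses rifampin and cyclosporine. A search on the Table 14-9 name returns only the permissive entry.

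The possible harm differs by drug:

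- **Nefazodone and ritonavir.** Section 1.2.1.1.3 warns that strong CYP3A4 inhibitors may amplify LEE011's main potential toxicities: myelosuppression, hepatic toxicity and QT prolongation.
- **Rifampicin.** Section 1.2.1.1.2 says that CYP3A4 inducers may affect LEE011 elimination, so the risk is under-exposure.
- **Cyclosporin A.** The same section says LEE011 may itself inhibit CYP3A4, so the risk is raised exposure to the co-medication.

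Patients may be as young as 12 months.

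**Working it through.** No design figure is involved. The check matches each caution list against the prohibited lists (Tables 14-6 and 14-10), treating rifampicin as rifampin and cyclosporin A as cyclosporine, and then looks for precedence text.

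**Step 1. Table 14-9 against Table 14-6.**

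| Table 14-9 (caution) | Table 14-6 (contraindicated) | Class banned in Section 6.4.3 |
|---|---|---|
| Cyclosporin A | cyclosporine | narrow-window CYP3A4/5 substrate |
| Nefazodone | nefazodone | strong CYP3A inhibitor |
| Rifampicin | rifampin | strong CYP3A inducer |
| Ritonavir | ritonavir | strong CYP3A inhibitor |

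The other six drugs (bosentan, fusidate, glibenclamide, lovastatin, sulindac, troglitazone) are in neither prohibited table. The overlap is 4 of 10.

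**Step 2. The other caution lists.**

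- Table 14-7 has two overlaps. Ritonavir is in its moderate-inducer row ("Bosentan, efavirenz, etravirine, modafinil, nafcillin, ritonavir, talviraline, tipranavir") and is prohibited in Table 14-6. Domperidone is in its moderate-inhibitor row and is excluded in Table 14-10.
- Tables 14-8 and 14-11 have none.
- In total, 4 + 2 = 6 entries overlap. Ritonavir is counted twice, so there are 5 distinct drugs.

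**Step 3. Precedence text for each overlap.**

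- *Table 14-7, 2 entries.* Footnote 1 sends the reader to Section 5.3. Criterion 14 (strong CYP3A4/5 inducers or inhibitors) reaches ritonavir, and criterion 13 (agents known to prolong QTc) reaches domperidone. Those criteria concern drugs the patient is receiving at entry, but the footnote is not itself limited to enrolment. It does not cite Section 6.4.3. Both entries are substantially covered.
- *Table 14-9, 4 entries.* There is no footnote.

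**Step 4. What is left.** 6 − 2 = 4 entries have no precedence text where they stand, all in Table 14-9. The Table 14-7 footnote already makes ritonavir contraindicated. So 4 − 1 = 3 drugs (cyclosporin A, nefazodone, rifampicin) have no precedence note on any caution list that names them.

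**The case against.** The strongest reply is that the rules do not conflict. Section 6.4.2 and Appendix 6 are organised by mechanism, and a drug with two mechanisms can properly appear in two tables. A caution about BSEP inhibition does not waive a CYP3A ban. Section 6.4.3 prohibits without exception, and Appendix 6 repeats the ban a few paragraphs before the BSEP table. Appendix 6 also calls its lists a guide and names a contact. In addition, Section 6.4.1 requires new medications to be reported to the site and allows other new medications to be discussed with the sponsor, and Section 6.4.2 requires careful monitoring of patients on caution-list drugs.

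Most of this stands. A careful reader would apply the stricter rule, and harm would require a site to consult one table alone and ask nobody. But Section 6.4.2 says more than that these drugs carry a BSEP risk: it says the listed drugs are permitted. The footnote on Tables 14-7 and 14-8 already recognises that a caution-list drug may be excluded on other grounds. It is missing from Table 14-9, which has the most overlaps. None of the safeguards says which entry governs a drug started during treatment, and the enrolment sentence in Appendix 6 does not address that case.

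A reader might go further and infer that all five overlapping drugs are left unresolved, or that the protocol actually authorises strong CYP3A inhibitors and inducers during treatment and so distorts the DLT data. The documents support neither. The Table 14-7 footnote substantially handles ritonavir and domperidone. Section 6.4.3 remains a flat ban, and nothing shows that any of these drugs was or would be used.

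**Conclusion.** The point holds as a minor safety-drafting correction. Four of the ten drugs in Table 14-9 are marked permitted with caution although Section 6.4.3 and Table 14-6 prohibit them, and the table lacks the precedence note that two neighbouring caution tables carry. For three of the four, no caution list naming them has such a note. Section 6.4.3 is the natural controlling rule, so the defect is a contradictory instruction within the protocol and does not leave the prohibition itself missing.

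The conclusion rests on two assumptions: that rifampicin and rifampin, and cyclosporin A and cyclosporine, are the same drugs; and that Table 14-9 has no footnote beyond what appears in the supplied text. The documents give no frequency of use for these drugs, so none is estimated, and no effect on dose finding, endpoints or analysis is claimed.

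**What to change.** Either change is enough:

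1. Delete cyclosporin A, nefazodone, rifampicin and ritonavir from Table 14-9.
2. Keep the table and add a footnote: any drug listed here that is prohibited under Section 5.3, Section 6.4.3, Table 14-6 or Table 14-10 remains prohibited throughout treatment.

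Two optional additions would help: cite Section 6.4.3 in the Table 14-7 footnote as well as Section 5.3, and use one name per drug across the tables.

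The cost is four deleted entries or one footnote at the next amendment. No endpoint, analysis set, model or sample size changes.
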